This is a single-center, prospective, ‘open-label,’ investigator-initiated pilot study evaluating the role of continuous glucose monitor (CGM) use either alone or with remote monitoring capabilities that enable subjects to share CGM data with family and friends (whom we will call “followers” in this protocol) among women with T1DM associated with pregnancy. We hypothesize that CGM use will decrease percentage of glucose values below the target range, decrease frequency of severe hypoglycemic episodes, and increase post-prandial glucose values into the target range, with a possible reduction in A1C compared to not using CGM during pregnancy. We hypothesize that the use of remote technology (**Share™ technology**) with subject’s designated follower will decrease hypoglycemia fear and the frequency of severe hypoglycemic episodes compared to CGM use alone in pregnancy or not using CGM use in pregnancy. This study aims to improve maternal glucose management among women with T1DM with a hope to also improve health outcomes during pregnancy.

The study will enroll up to 40 patients from the Barbara Davis Center for Childhood Diabetes (BDC) Adult clinic over the age of 18 years who are pregnant (13 weeks gestation or less) or plan to become pregnant within the following 6 months. The study will also attempt to enroll up to 40 followers (one per pregnant subject) who are family members or friends of the pregnant subjects and over the age of 18 years. All subjects meeting these criteria will be invited to sign informed consent and participate in the study. All pregnant subjects will be stratified into one of three groups: (1) CGM use alone, (2) CGM use with Share™, (3) no CGM use. CGM use will be offered to all subjects, but individuals who do not want to wear a CGM will be stratified to Group 3. Stratification for Groups 1 and 2 will depend on the following: subjects and followers who have iPhones, iPads, and/or iPod touches will be placed into Group 2 which requires one of these devices to function, while all others will be placed in Group 1. All subjects will be followed for study visits with similar frequency during the pregnancy, and subjects in Groups 1 and 2 will wear the Dexcom G4 Platinum® CGM system from the first pregnancy visit until delivery. All subjects in Group 2 will also use the Share™ technology from the first pregnancy visit until delivery.

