outcomes over the course of the pregnancy while diabetes control is managed per usual care (Group 1 for women using a non-Dexcom CGM such as Medtronic Enlite CGM or Group 3 for no CGM use). A PRA will maintain an active list of individuals and will update the list continuously as women are assigned into groups. All subjects will have similar clinical visits throughout the pregnancy.

Subjects stratified to Group 2, CGM use with Share™, will be asked to designate followers who will be able to view glucose trends and receive alerts for high or low sensor glucose values on an iPhone, iPad, iPod touch, and/or other compatible device. While multiple followers are allowed, one will be the main follower and will be invited to sign informed consent at the screening visit or within the first two months of each subject's study participation. Subjects stratified into Groups 1 and 3 will be asked to designate a main follower who may be aware of a subject's extreme glucose values (lows or highs) through contact with her and who may intervene on her behalf in such cases and will be invited to sign informed consent at the screening visit or within the first two months of each subject's study participation.

What are the treatment groups?

There will be three 'open-label' treatment arms consisting of routine care in the Pregnancy and Women's Health clinic at the BDC (no CGM use), an intervention arm using the Dexcom G4 or G5 Platinum® CGM system during pregnancy, and an additional treatment arm using the Dexcom G4 or G5 Platinum® CGM system with Share™ remote monitoring capabilities during pregnancy. As this is a non-randomized study and most women will opt to be in the Dexcom alone or Dexcom Share groups, we will include pregnant no CGM users identified through a retrospective chart review into the no CGM arm of the study.

How many subjects per treatment arm?

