Women in Group 2 will be trained in the use of the Share™ technology. They will be asked to designate a main follower and up to 4 additional followers who will receive access to sensor glucose data remotely through the secure, wireless communication system. Recommendations will be made for low and high glucose sensor alerts that will be individualized to each subject's needs (for example a low glucose alert with a higher glucose value for subjects with hypoglycemia unawareness compared to those without it). The main follower for each subject will be approached and asked to sign informed consent at Visit 2 or within 2 months of the subject's first pregnancy visit. Study participation of a main follower will be encouraged but not obligatory.

Women unwilling to wear a CGM but willing to participate in the study (Group 3) will be asked to check SMBG at least 7 times daily (fasting, before each meal, and 2 hours after meals, and at bedtime), per standard of care, for the duration of the study. All 3 groups will receive education about diabetes during pregnancy.

Women in Groups 1 and 3 will be asked to designate a main follower who will not receive data through a device, but rather through contact with the subject. The main follower for each subject (Groups 1 through 3)

will be approached and asked to sign informed consent at Visit 2 or within 2 months of the subject's first pregnancy visit. Study participation of a main follower will be encouraged but not obligatory.

Data on all subjects for medical history, existing diabetes complications, medications, vital signs, height/weight, A1C (current and most-immediately pre-conception), insulin doses, glucometer downloads, insulin pump downloads (if applicable), CGM downloads (if applicable), and adverse events (AEs) will be collected. If the woman was seen at the Barbara Davis Center prior to the consent visit, we will do a retrospective chart review for medications, vital signs, height/weight, A1C, insulin doses, glucometer downloads, insulin pump downloads (if applicable), and CGM downloads (if applicable) for the most-immediate pre-conception clinic visit and for visits during the current pregnancy. Each subject will be given a hypoglycemic fear questionnaire. We will ask women about interventions that have taken place over the last month for extremely low and high glucose values, directed by patient or a third party, and keep the information on research source documents.

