CGM: Continuous glucose monitoring is an FDA approved technology that offers a unique and practical way of identifying and differentiating clinical benefits of intensive diabetes care. The American Diabetes Association currently recommends CGM use during pregnancy for high-risk individuals (2). We currently have hundreds of patients, which include many pregnant patients, in the Adult Clinic at The BDC using CGM on a regular basis as part of usual medical management of their diabetes. Subjects may experience pain at the site of sensor insertion. The adhesive pads for the sensor may cause skin erythema for 1 to 2 days or more. An allergic reaction to 1 or more parts of CGM devices may occur which can be mild, moderate, or severe (rare). In rare cases, an infection at the sensor site may occur. In rare cases, the sensor or needle may break inside the body and would require a minor surgical procedure to remove it.

Data Collection Tools:

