The primary endpoints are glucose variability and changes detected by hypoglycemic fear survey. We will measure indices of glucose variability (mean glucose \pm SD, % of glucose within/above/below target ranges, J Index, High Blood Glucose Index [HBGI], Low Blood Glucose Index [LBGI], Mean Amplitude of Glycemic Excursions [MAGE], CONGA_n) throughout pregnancy using the SMBG 7-point profiles for one week taken once per trimester. Hypoglycemic fear survey results will be assessed once monthly over the pregnancy. We will compare outcomes within individuals over time and between individuals of the different study arms. We will test whether outcomes differ between women using Dexcom alone and women using Dexcom with Share™ using interaction terms, and will stratify analyses if differences by group are greater than 10 mg/dL in mean glucose levels are detected. Since SMBG logs will be taken at multiple time points over the pregnancy and since CGMs will be worn continuously for the duration of each pregnancy, linear mixed models will be used to assess changes in outcome measures (GV, time spent in target below or above target) over time in each trimester of pregnancy. We will use linear mixed models to assess changes in the hypoglycemic fear survey in each month of the pregnancy. Secondary endpoints include A1C differences among study arms. Improvement in glycemic variability parameters with a possible reduction of A1C by 0.3%, measured as the difference of the mean A1C laboratory values of the arms of the study between baseline (0-3 months, first trimester), second trimester (3-6 months), and third trimester (6 to 9 months). Mixed models account for missing data, allow for an unstructured covariance matrix for repeated measures, and account for inter-subjects correlation of measurements. Secondary outcomes will be used

in the same mixed models. Differences in frequency of low alert glucose rates, high alert glucose rates, and interventions for low or high glucose values among the followers for each study arm will be analyzed with student t-tests. A p-value < 0.05 will be considered significant, and we will perform statistical analyses with SAS software (version 9.3, SAS Institute, Cary NC).

Publication Strategy:

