Appendix B

Baseline Participant Questionnaire

Subject ID: _____ Study Visit: (dd/mmm/yyyy) : _____ / _____ / _____

DEMOGRAPHIC INFORMATION

Date of Birth _____
(dd/mmm/yyyy)

Ethnicity

- Asian/Oriental
- African American
- Caucasian
- Hispanic or Latino
- Other

If other, specify _____

Education

- Grade school
- High School/GED
- Some College
- Associates degree
- Bachelor's Degree
- Master's degree
- Other

If other, specify _____

Marital Status

- Single
- Married
- Widowed
- Other

If other, specify _____

DIABETES HISTORY

Duration of Diabetes: _____

Immediate family history of diabetes? Yes No

Method of Insulin delivery:

- MDI
- Pump Therapy
- VGO Insulin Therapy

Type and Average Dose of Insulin Used:

Basal: _____ Dose _____

Bolus: _____ Dose _____

Other Diabetes medications? _____

If yes, specify _____

CGM Use: Current CGM user If yes, duration of previous use _____
 Past CGM user
 Never used CGM

DIABETIC COMPLICATIONS

Diabetic Retinopathy? Yes No Unknown

Diabetic sensory or motor neuropathy? Yes No Unknown

Diabetic autonomic neuropathy? Yes No Unknown

Diabetic nephropathy? (including micro-albuminuria) Yes No Unknown

If yes, please specify the most recent event diagnosed at the time of patient inclusion:

Impaired renal function (estimated GFR by MDRD below 60mL/min)

Micro-albuminuria (30-299mcg per mg creatinine)

Overt proteinuria (equal to or above 300 mcg per mg creatinine)

High Cholesterol? Yes No Unknown

High Blood Pressure? Yes No Unknown

PRE-EXISTING CONDITIONS

Does the subject have any pre-existing conditions? Yes No

If yes, list below

CONCOMITANT THERAPY

Is the subject taking any medications other than insulin? Yes No If yes, list below

PREVIOUS OBSTETRIC HISTORY

Past pregnancy? Yes No
If no, skip to next section.

Fill out information for each pregnancy. If there are more than 4 pregnancies, continue on another sheet.

First Pregnancy

Outcome Date _____
(dd/mmm/yyyy)

Delivery type:

Vaginal 	If yes: Spontaneous 	Induced 	Breech 	Vacuum 	Forceps 
VBAC 	If yes: Spontaneous 	Induced 			
Cesarean Section 	If yes: Low Transverse 	Low Vertical 	Classical 	Unspecified 	

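### Arms are formed by device ownership, willingness to wear CGM and chart review, but the planned between-arm tests name no adjustment for baseline differences

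*Combined protocol and SAP*

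**What the plan says.** **How arms are formed.** The opening summary says that "subjects and followers who have iPhones, iPads, and/or iPod touches will be placed into Group 2 which requires one of these devices to function", and that "individuals who do not want to wear a CGM will be stratified to Group 3"; all others go to Group 1. The recruitment section repeats the device rule, allows the follower some other compatible device, and adds one more route for women who do not want a Dexcom: "Group 1 for women using a non-Dexcom CGM such as Medtronic Enlite CGM". The section on subjects per arm expects 10, 20 and 10 prospective women in Groups 1, 2 and 3. It then adds up to 30 women to Group 3 from chart review, whose pregnancies fell around the time of enrollment or before the study began.

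**How arms are compared.** The Statistical Analysis Plan states: "We will compare outcomes within individuals over time and between individuals of the different study arms". It uses linear mixed models for glucose variability, the fear survey and A1C, t-tests for follower outcomes, and p < 0.05 throughout. It credits the mixed models with handling missing data, covariance and correlation. It names no baseline covariate, propensity score, matching, weighting or sensitivity analysis.

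**What is recorded.** Appendix B has education, marital status, diabetes duration, "Method of Insulin delivery", prior CGM use and complications. Visit 2 adds current and pre-conception A1C and a fear survey. Under *Control Arm*, chart-review women contribute clinical chart data, including A1C from the last pre-conception visit, insulin doses and pump downloads. They complete no questionnaires.

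**The concern.** Women who own particular devices, women who refuse a sensor, and women found in old charts can differ in ways that affect glucose control and fear of hypoglycemia whatever device they use. The chart-review women add two further differences. Some were treated in an earlier period, and they enter only if they respond when contacted after pregnancy. Without adjustment, a between-arm p-value tests the sum of the device effect and these differences. This reaches both primary endpoints: glucose variability in every contrast, and the fear survey among the prospective women.

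At stake is how the pilot is read. The protocol states comparative hypotheses for CGM and for Share, plans publication, and intends to use what it learns to plan a larger randomized study. A spurious arm difference, or one hidden by selection, would carry into that planning.

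**Working it through.** **1. The plan's own figures reproduce.** 10 + 20 + 10 = 40 prospective women. Drop-out of 20% gives 40 × 0.20 = 8, leaving 32. There is no power calculation to check.

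**2. Make-up of Group 3.** Ten prospective plus up to 30 retrospective women gives up to 40. The retrospective share is 30/40 = 75% of Group 3 and 30/70 = 43% of all women. In the CGM versus no-CGM contrast (30 versus up to 40), chart-review women can be three quarters of the comparator.

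**3. Does anything in the plan already adjust?** Three items come close.
- The interaction terms and the 10 mg/dL rule for stratifying concern outcome differences between Groups 1 and 2. They do not address baseline differences.
- Intention to treat does not balance groups that were never randomized.
- Within-woman comparison could remove stable level differences, but the plan does not define an arm-by-time contrast as the test. Its A1C baseline is the whole first trimester, while CGM starts at the first pregnancy visit and some women already wear one.

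**4. Which covariates exist for whom.**

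| Variable | Prospective women | Chart-review women |
|---|---|---|
| Pre-conception A1C | yes | yes (last pre-conception visit) |
| Insulin delivery (MDI/CSII) | yes | derivable from medications, insulin doses and pump downloads |
| Diabetes duration | yes | where charted |
| Prior CGM use, education | yes (Appendix B) | no questionnaire |
| Fear score at Visit 2 | yes | none |
| Income, motivation | no | no |

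One covariate list therefore cannot serve every contrast. Requiring education in CGM versus no CGM would drop the chart-review women.

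**5. Illustrative scale.** The documents give no imbalance, correlation or SD, so these inputs are assumed. For one confounder, bias in SD units = standardized imbalance × correlation with the outcome:
- 0.5 × 0.3 = 0.15 SD
- 0.5 × 0.6 = 0.30 SD

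With no true effect, a two-sided 5% t-test has noncentrality bias / √(1/n₁ + 1/n₂). The rejection rates are:

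| Contrast | Bias 0.15 SD | Bias 0.30 SD |
|---|---|---|
| Group 1 vs 2 (10 vs 20) | 6.6% | 11.6% |
| CGM vs no CGM (30 vs 40) | 9.4% | 23.2% |

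These rates apply to a comparison of levels at full planned numbers. Stable differences would weigh less in a contrast of within-woman change.

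**6. Does adjustment help?** A simulation (20,000 runs per setting, no true effect) used one measured confounder imbalanced by 0.5 SD and correlated 0.3, 0.5 or 0.7 with the outcome. Unadjusted false-positive rates were 6.4%, 9.7% and 14.3% for 10 versus 20 women, and 9.2%, 17.6% and 29.1% for 40 versus 30. With that covariate in the model, bias was about zero and the rate about 5% in every case. This shows only that measured confounding can be removed.

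**The case against.** The strongest reply is that this is a declared non-randomized pilot without formal power, that *Weakness of the Study* admits as much, and that no adjustment can deliver causal attribution when income and motivation are unmeasured. This stands, and it limits the severity. It does not supply an analysis: the plan still tests arm differences at p < 0.05 while leaving recorded baseline data unused.

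A second reply is that the models may target change over time. That would remove stable level differences, though not differences in trajectory, and the plan does not commit to it.

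Several stronger readings are tempting but lack support in the documents:
- **That support at home decides Group 2.** Women in all three groups are asked to name a main follower. Device possession separates Groups 1 and 2.
- **That hypoglycemia risk or unawareness drives CGM uptake.** The protocol notes that the diabetes association "currently recommends CGM use during pregnancy for high-risk individuals", but this study offers CGM to everyone and supplies sensors. Unawareness appears only as an example of setting alerts ("a low glucose alert with a higher glucose value for subjects with hypoglycemia unawareness compared to those without it"), and nothing links it to uptake.
- **That the models contain only arm, time and their interaction.** The plan does not list its model terms. What can be said is that it names no covariate.
- **That the needed confounders are recorded for everyone.** Chart-review women have no questionnaire data. Gestational age at entry is an eligibility check and is not in the Visit 2 data list; the Appendix B gestational-age fields concern earlier pregnancies.
- **That bias could account for a stated share of the hoped-for 0.3% A1C reduction.** This needs an assumed SD on top of the assumed imbalance and correlation, and A1C is a secondary endpoint.

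**Conclusion.** The gap is real. Arms are formed by patient characteristics, up to 75% of Group 3 may be chart-review women, and between-arm tests are planned with no named adjustment although usable baseline data exist. Arm differences under this plan cannot be read as effects of CGM or Share.

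The size cannot be derived from the documents. Under the stated assumptions it is 0.15 to 0.30 SD in levels, and less for stable differences if change within women is the contrast. Neither the direction nor the actual imbalance is known.

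This should be fixed before analysis. The declared pilot status keeps it from being fatal. Even after the fix the contrasts remain associations, because adjustment reaches only what was measured.

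**What to change.** Add to the Statistical Analysis Plan a short fixed covariate set for each contrast.

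**(a) CGM versus no CGM, glycemic outcomes.** Adjust for pre-conception A1C, insulin delivery (MDI/CSII), and diabetes duration where charted. Use pre-conception A1C as the A1C baseline in place of the first-trimester value. State a rule for women with a missing value. Add a sensitivity analysis restricted to prospectively enrolled women.

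**(b) Share versus CGM alone, and all fear-survey contrasts (prospective women only).** Adjust for the Visit 2 fear score (fear endpoint) or pre-conception A1C (glycemic endpoints), prior CGM use, and one further item such as education collapsed to two levels. Prior CGM use matters because, in women already wearing a sensor, these baseline values may already reflect CGM.

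Show unadjusted results as descriptive. Report every arm contrast, including the follower t-tests, as an association, and say that income and motivation were not measured.

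**Cost.** A paragraph of plan wording and no new data collection. Set (a) uses 1 + 1 + 1 = 3 degrees of freedom. Set (b) uses 3, or 4 if prior CGM use keeps its three categories. With 32 completers and three arms, about 32 − 3 = 29 between-woman degrees of freedom fall to 25 or 26. For Share versus CGM alone, if drop-out is even across arms, 30 × 0.8 = 24 completers give 24 − 2 = 22, falling to 18 or 19. Expect somewhat wider intervals with about 10 women in the smallest prospective arms. For the same reason the list should not grow, and a propensity model on a long list would be unstable.

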CGM data will be analyzed for mean blood glucose values, time spent in hyperglycemic (>240, >300mg/dl) and hypoglycemic (<50, <70, <80 mg/dl) ranges and various indices of glycemic variability. Laboratory analysis for A1C will be performed at baseline, monthly thereafter during the pregnancy, and post-partum. Routine blood tests will be performed in all subjects in each trimester (see Table 1).

Primary outcomes will be:

- 1) Glucose variability as measured by glucose excursions from self-monitoring blood glucose (SMBG) data through log books and downloads as well as CGM downloads and various indices [J-index, mean amplitude of glycemic excursion (MAGE), high blood glucose index (HBGI), low blood glucose index (LBGI)] from CGM downloads.
- 2) Changes detected by the hypoglycemia fear questionnaire.

Secondary outcomes will be:

- 1) How CGM alone and CGM with Share™ usage affect A1C compared to no CGM use,
- 2) Progression of diabetes complications (retinopathy, nephropathy),
- 3) Maternal and fetal outcomes (eclampsia/pre-eclampsia, live birth rates, birth weight, neonatal hypoglycemia, and other similar measures).

Introduction:

Among the US population, 29.1 million people (9.3%) have diabetes (1). Pre-existing diabetes has to be managed very carefully throughout pregnancy to optimize maternal and fetal outcomes (2). Among women

with T1DM who are pregnant, the tools that we have to regulate maternal glucose control include multiple daily injections (MDI), continuous subcutaneous insulin infusion therapy (CSII) also known as insulin pump therapy, and for high-risk individuals continuous glucose monitoring (CGM) (2). CGM use in pregnancy has been shown to be safe, to reduce the frequency of severe hypoglycemia, and to improve A1C values (3-6). Sensor-augmented pump therapy with CGM use continuously was shown to lower A1C more than intermittent use in pregnant women with T1DM (7). However, few studies have measured changes in glucose variability that occur with CGM use during pregnancy and no studies have evaluated how tools that allow family and friends (followers) to access glucose trends affect outcomes during pregnancy.

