A total of up to 40 pregnant women will be prospectively recruited into the study. As this is an 'open-label' study whose group stratification is based on subject characteristics (willingness to wear CGM, subject possession of iPhone, iPad, or iPod touch, follower possession of iPhone, iPad, or iPod touch), we cannot predict the number of subjects per treatment arm. Based on our current pregnant population's willingness to use CGM and device usage, we anticipate that 10 subjects will be in Group 1, 20 subjects in Group 2, and 10 subjects in Group 3. We will include up to 30 additional women in Group 3 identified through a retrospective chart review who were pregnant around the time of study enrollment and before the study began.

In addition, there will one main follower for each prospectively enrolled pregnant subject (up to 40 adults) who will be asked questions once per month about knowledge of the subject's glucose trends and interventions that s/he may have done on her behalf over the last month.

What is the schedule of events for the treatment groups?

After screening, when pregnancy is confirmed subjects will be stratified to Group 1, 2, or 3. Subjects in all groups will have similar study/clinic visits for data acquisition at the screening, pregnancy visits (which occur a minimum of monthly throughout gestation), and post-partum clinic visit. All subjects will be required to test blood glucoses at least 7 times a day throughout pregnancy. All subjects will be asked to log the SMBG values 7 times a day with insulin doses for meals for 1 week every trimester of the pregnancy.

Subjects stratified to CGM wear will be provided with a Dexcom G4 CGM, transmitter, and sensors (4 per month). Subjects stratified to CGM wear who want to use their personal Dexcom G5 devices will be asked to provide Dexcom mobile usernames (if they use G5 with an iPhone) and will be provided with sensors (4

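### Percent of readings below range gets a linear mixed model with no provision for variance differing by arm; if CGM at least halves the rate, the 95% intervals are the wrong width, in a direction that depends on whether the retrospective women enter

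*Combined protocol and SAP*

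**What the plan says.** The study summary puts the hypoglycemia hypothesis first: CGM use will "decrease percentage of glucose values below the target range". The Statistical Analysis Plan lists among the primary glucose-variability indices the percentage "of glucose within/above/below target ranges, J Index, High Blood Glucose Index [HBGI], Low Blood Glucose Index [LBGI"] and others, measured "throughout pregnancy using the SMBG 7-point profiles for one week taken once per trimester". Appendix D is that log: seven days, with values before and two hours after three meals and one at bedtime. For the model it says that "linear mixed models will be used to assess changes in outcome measures (GV, time spent in target below or above target"). It adds that mixed models "allow for an unstructured covariance matrix for repeated measures, and account for inter-subjects correlation of measurements". It names no link function, transformation, weighting by number of readings, robust standard error or variance by study arm.

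The list of primary outcomes takes glucose variability more widely from "self-monitoring blood glucose (SMBG) data through log books and downloads as well as CGM downloads". On numbers, the section on subjects per treatment arm says "we anticipate that 10 subjects will be in Group 1, 20 subjects in Group 2, and 10 subjects in Group 3", and then adds up to 30 no-CGM women from chart review. The Control Arm section gives those women meter downloads and describes no 7-point log week for them.

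**The concern.** A percentage of 49 readings moves in steps of about 2 points and is often zero when lows are rare. Its variance is close to proportional to p(1 − p), so the arm with more lows has the larger spread. An unstructured covariance over repeated measures lets the variance differ between trimesters. It does not let it differ between arms unless that is requested. With one covariance for all arms, the standard error of a contrast is right only if the arm variances are equal or the arm sizes happen to compensate.

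If the hypothesis is true, the arms do differ in variance. This is a pilot without formal power that is meant to inform a larger trial, so the estimates and their intervals are its main product. They would be mis-sized in the situation that the study hopes to find.

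**Working it through.** **Inputs from the documents.** Readings per log week: 7 × 7 = 49, so one reading is 1/49 = 2.0 percentage points. Prospective arms (CGM alone / Share / no CGM): 10/20/10. Drop-out 20%: 40 × 0.80 = 32, as the plan states, or 8/16/8. With all retrospective women: 10/20/40. The documents give no rate below range and no effect size.

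**Assumptions.** True rates of 1 to 8% below range, three logs per woman, beta-binomial counts with the same between-woman precision φ in every arm (15 or 30). With independent readings, the chance of a week with no low value is 0.99^49 = 0.61 at a 1% rate and 0.98^49 = 0.37 at 2%.

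**Formula.** Under these assumptions the variance of a woman's mean is v = c·p(1 − p), with c the same in every arm, so c cancels. Let v0 refer to no CGM and v1 to CGM, with the two CGM arms taken together for the contrast.

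- True variance of CGM minus no CGM: v0/n0 + v1/n1.
- Variance that the pooled model reports, on average: s² × (1/n0 + 1/n1), where s² is the df-weighted mean of the arm variances.
- Width ratio: the square root of reported over true. Approximate coverage: 2Φ(t × ratio) − 1.

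**8% v 4% at 10/20/10.** v0 = 0.08 × 0.92 = 0.0736; v1 = 0.04 × 0.96 = 0.0384.
- True: 0.0736/10 + 0.0384/30 = 0.00864.
- s² = (9 × 0.0736 + 28 × 0.0384)/37 = 0.04696. Reported: 0.04696 × (1/10 + 1/30) = 0.00626.
- Ratio √(0.00626/0.00864) = 0.851. With t(37) = 2.026, coverage is about 92%.

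**8% v 4% at 10/20/40.**
- True: 0.0736/40 + 0.0384/30 = 0.00312.
- s² = (39 × 0.0736 + 28 × 0.0384)/67 = 0.05889. Reported: 0.05889 × (1/40 + 1/30) = 0.00344.
- Ratio 1.049. With t(67) = 1.996, coverage is about 96%.
- CGM alone v Share: √(0.05889/0.0384) = 1.238, coverage about 98.7%. At 10/20/10 the same contrast is also too wide, by less: √(0.04696/0.0384) = 1.106, about 97.5%.

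The same steps for other rates, beside simulations of the pooled-variance contrast on woman means (6,000 to 20,000 runs per cell; 8/16/8 for the prospective rows, 10/20/40 for the others):

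| Layout and contrast | No CGM v CGM | Width ratio | Formula | Simulated |
|---|---|---|---|---|
| 10/20/10, CGM v none | 8% v 6% | 0.935 | 94% | about 94% |
| 10/20/10, CGM v none | 8% v 4% | 0.851 | 92% | 90–91% |
| 10/20/10, CGM v none | 4% v 1% | 0.734 | 86% | 82–84% |
| 10/20/40, CGM v none | 8% v 4% | 1.049 | 96% | about 96% |
| 10/20/40, alone v Share | 8% v 4% | 1.238 | 98.7% | 97–99.7% over all scenarios |

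At 8/16/8, the cells 8% v 3% and 6% v 2% gave 88% and 86 to 87%. With no effect, coverage was 95 to 96%. Over all small-layout cells with the rate halved or more, the range is about 81 to 91%.

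**Check with fitted models.** Random-intercept mixed models with 20% drop-out (200 runs each) gave 89% for 10% v 5% at 10 v 30, 95% with no effect, and 97.5% for 10% v 5% at 40 v 30. The Monte Carlo error at 89% is √(0.89 × 0.11/200) = 2.2 points.

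**What the alternatives do.**
- Arm-specific variances: 89 to 94% at 8/16/8, and 94 to 96% once 20 or more retrospective women enter.
- Empirical logit: 92 to 97% at the small layouts, except 88 to 90% in the rarest scenario (4% v 1%).
- Power for 8% v 4% at 10/20/40 with the greater between-woman spread (φ = 15): 0.87 on the empirical logit against 0.76 on the linear scale.

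**The case against.** The strongest objection is the arm layout. The protocol adds up to 30 women to the no-CGM arm, which would make it the larger arm. With 10 of them added to 8/16/8, coverage for CGM versus no CGM is 91 to 94%; with 20 it is 95 to 96%; with all 30 it is 96 to 97%. This stands, and it rules out any flat statement that the interval under-covers. It does not clear the model, because the same pooling then makes the CGM-alone versus Share interval too wide. The documents also leave the layout open: the indices are tied to logs that the retrospective women are not described as keeping, while the primary outcome list also names meter downloads.

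A reader might infer that the fault is treating a small count as normal. The calculations do not support that as the main cause: with balanced arms (30 v 30) the same count out of 49 gives 95% coverage. The cause is unequal variance combined with unequal arms, so a change of scale is one remedy among several.

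Three further points stand. A common variance is inferred from silence; the SAP does not exclude variance by arm. CGM time below range is not a count out of 49, and no coverage was computed for it; but women without CGM have only SMBG readings, so CGM versus no CGM must rest on SMBG. Finally, self-selection into the arms is a larger threat to this comparison than a few points of coverage. That limits the weight of this point, but the correction remains cheap.

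**Conclusion.** The point holds conditionally. The SAP applies a linear mixed model to a bounded outcome whose variance follows its mean, and makes no provision for variance differing by arm.

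- If only prospective women enter (about 10/20/10, or 8/16/8 after drop-out) and CGM cuts the rate by half or more, the 95% interval for CGM versus no CGM covers about 81 to 91%. Smaller effects cost little: about 94% at 8% v 6%.
- If all 30 retrospective women enter (10/20/40), that interval is about nominal (96%). The CGM-alone versus Share interval covers 97 to 99.7%, and power for CGM versus no CGM is lower than on the logit scale.

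These figures rest on assumed rates, beta-binomial spread with a common φ, and one covariance for all arms. A reader might infer that the trial's interval simply does cover 80-odd percent, or that its p-values are too small when CGM has no effect. Neither follows: the documents give no rates and leave the layout open, and under no effect the test keeps its 5% level. This is a cheap improvement to the SAP, not a flaw that invalidates the analysis.

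**What to change.** In the Statistical Analysis Plan, name the model for readings below (and above) range:

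1. Analyse the number of readings below range out of readings recorded with a binomial mixed model that allows overdispersion, or with a mixed model on the empirical logit weighted by readings. Use small-sample degrees of freedom. Report odds ratios with model-based percentages for each arm.
2. Alternatively, keep the linear scale as the percentage-point analysis, with arm-specific variances: in SAS, a group-specific covariance with Satterthwaite or Kenward-Roger degrees of freedom.
3. State whether the retrospective women's meter downloads enter this analysis, and how differing numbers of readings per woman are handled.

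The cost is a paragraph of SAP text and a different model specification. No extra women, visits or data are needed. The downside of option 1 is a ratio-scale effect, which is why the percentages should be reported beside it. Neither option fully restores coverage when lows are very rare and the no-CGM arm is small, and the report should say so.
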